7.1.10. Missing data

1. Days with missing data will not be ignored when defining start of an e-diary signal: e.g., if a patient has two qualifying symptoms followed by a missing day, if the next day with data has two qualifying symptoms this will not be defined as an exacerbation. Hence, the start of an e-diary signal of an exacerbation will require 2 consecutive non-missing days of worsening. If there is partially recorded symptom data at a visit, however, only the observed values will be considered but the day will not be discarded.
2. Days with missing data will be ignored when defining end of an e-diary signal of an exacerbation: e.g., if a patient has two days missing in the baseline period and one day missing in the 3- day moving average, both baseline and 3-day moving average values will be calculated using observed data only. Similar rules will apply when there is partially recorded symptom data at a visit (and daily average values will be calculated among the observed values).
3. All available data will be used for each patient.
4. As a general rule, the baseline symptom count score, and 3 day moving averages are calculated as the average count score of the observed days in the baseline

Study alias & e-track number(s): NTHi-004 (200157)

period. For example, if an **e-diary** signal occurs from day 10 onwards, the baseline period will be the average between day1 and day2 (day1 being the first study day). If day 13 is missing, the 3 day moving average at day 14 will only take into account day 14 and day 15.

5. If there are greater than 2 consecutive days of missing data after an **e-diary** signal not resolved, the **e-diary** signal will not be considered resolved until the next day with observed data if the corresponding moving average is below the baseline value. In other words, if the 3-day average daily score is missing, the day will be counted in the duration of the episode.

7.1.11. AECOPDs definitions and calculation rules

7.1.11.1. AECOPD definition (from clinical evaluation)

Due to the sensitivity and specificity of the e-diary device, false alerts may occur, and exacerbations resulting in site visits may also occur without e-diary alert. Therefore, only unscheduled AECOPD visits with clinical confirmation of AECOPD (with or without associated signals) will be considered as AECOPD events in the primary analysis.

In addition, missed AECOPD visits may have occurred and can be:

- a signal from the e-diary (PHT) without a site visit but that cannot be discounted as a possible exacerbation signal after reconciliation,

and/or

- an exacerbation reported retrospectively in the Safety database or medical records for which there has not been in the same period of retrospective reporting a corresponding exacerbation visit declared.

7.1.11.2. Characterization of inconsistencies between morning e-diary signals and exacerbation site visits

The reconciliation between morning e-diary (PHT) signals and site visits for exacerbation will aim at characterizing the following 2 cases:

Case A : an e-diary alert with absent/delayed exacerbation visit (i.e. no exacerbation visit within the calculated length of the e-diary episode)

Case B : a exacerbation visit with absent/delayed e-diary exacerbation alert (i.e. RDE exacerbation not within e-diary exacerbation period)

The different reasons of inconsistencies of Case A will be categorized by the site after review according to the following explanation:

Statistical Analysis Plan

Study alias & e-track number(s): NTHi-004 (200157)

- 1) *Not an exacerbation after further evaluation* : eg. when a patient does not feel well but this is due to increased exercise, or patient does not feel well but this is not clinically significant.
- 2) *Ongoing exacerbation* : e.g., previous exacerbation is not terminated according to the clinician.
- 3) *RDE or other technical issues*: e.g., due to technical issues e-diary alerts were not sent and when the site was aware of it was too late to determine whether this was an exacerbation or not.
- 4) *Other reasons: specify* : e.g. subject was on holidays / subject unable to visit the site / delayed RDE visit/early RDE entry.

The different reasons of inconsistencies of Case B will be categorized by the site after review according to the following explanation:

- 5) *Spontaneous visit clinically deemed exacerbating* i.e. exacerbation visit took place before the e-diary alert (spontaneous visit, visit triggered by GP / Patient call asked to be seen/ felt too unwell to complete e-diary abrupt onset)
- 6) *Planned monthly visit clinically deemed exacerbating*
- 7) *e-diary diary card recording issue or other technical issues* : e.g. late e-diary alerts, subject missed or did not correctly record diary card, broken log pad device.
- 8) *Other reasons: specify*

For a Case A, no laboratory data has been collected, but if the answer about the inconsistency is 3) or sometimes 4) (depending on the specification), it will qualify as AECOPD. All Cases B will be considered to be an AECOPD if the AECOPD is confirmed by the site.

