6.5.4. Intervals between study visits

Table 9 Intervals between study visits

Interval	Optimal length of interval	Allowed interval
Scheduled study visits		
Screening Visit completed → Visit 1	14 - 28 days ¹	14 - 28 days ¹
Visit 1 → Visit 2	7 days	7 - 9 days
Visit 1 → Visit 3	30 days	30 - 45 days
Visit 1 → Visit 4	60 days	60 - 75 days ²
Visit 4 → Visit 5	7 days	7 - 9 days
Visit 4 → Visit 6	30 days	30 - 45 days ²
Visit 6 → Visit 7	90 days	90 - 120 days
Visit 6 → Visit 8	180 days	180 - 210 days ³
Visit 6 → Visit 9	270 days	270 - 300 days
Visit 6 → Visit 10	360 days	360 - 390 days ³
AECOPD-driven study visit(s) and/ or phone contacts		
Onset of AECOPD symptoms as recorded in the electronic Diary Card or confirmed by the subject → AECOPD Visit	-	max 96 hours ⁴
Interval between AECOPD Visit and scheduled study visit		
AECOPD visit → scheduled study visit	-	min 7 days ⁵

¹Visit 1 should take place 14 - 28 days after Screening completed. If for an eligible subject, a delay occurs so that the interval between Screening completed and Visit 1 exceeds 28 days, the entire Screening Visit needs to be repeated.

²Subjects will not be eligible for inclusion in the according-to-protocol (ATP) cohort for analysis of immunogenicity if they make the study visit outside this interval.

³Subjects will not be eligible for inclusion in the ATP cohort for analysis of persistence of immunogenicity if they make the study visit outside this interval.

⁴AECOPD visits will be scheduled as soon as possible after the onset of AECOPD symptoms as recorded in the electronic Diary Card or confirmed by the subject (maximum 96 hours after and, if applicable, preferably before starting treatment with antibiotics).

⁵Scheduled study visits should not take place within 7 days of an AECOPD visit. If an AECOPD occurs at the time of a scheduled study visit so that this is not adhered to, the scheduled visit should be re-scheduled to a later date within the time window specified. In consultation with GSK, only Visit 10 (Day 450) may exceptionally be conducted outside of the allowed interval if necessary.

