5. Only symptom data collected during the study period will be used to define the start of an exacerbation.

7.1.8. End/Duration of an e-diary signal of an exacerbation:

1. The end/recovering of an e-diary signal of an exacerbation corresponds to the day at which the 3-day moving average of the daily symptom count score (average between the day the day before and the day after) to return to baseline symptom count score (the mean daily symptom count score over days 14 to 8 preceding exacerbation onset). For a specific day, the daily symptom count score is defined as the sum of the symptom scores experienced in this day (a major symptom accounts for 2 points, a minor symptom accounts for 1 point, as in Trappenburg *et al.*, 2011, but contrary to Seemungal *et al.* 2000 and Mackay *et al.* 2014, in which all symptoms accounted to 1). Note that the symptoms that have occurred consecutively for 5 days or more prior to a potential exacerbation and that are discarded for these exacerbations are not discarded from the symptoms counts.
2. The length of an e-diary signal of an exacerbation will be at least of 2 days. So rule 1 will only apply from the third day onwards.
3. The baseline symptom count score is calculated as the average count score of the observed days in the period used to calculate the baseline symptom count score. For example, if an exacerbation occurs from day 10 onwards, the

Statistical Analysis Plan

Study alias & e-track number(s): NTHi-004 (200157)

baseline period will be the average between day1 and day2 (day10 - 8 days= day2, day10 - 9 days = day1, Day1 being the first study day). For exacerbations before day 9 but after day 2, the baseline symptom score will be considered to be day1

4. If the first e-diary signal of an exacerbation is occurring before day 3: duration will be counted until the day in which there is at most 2 majors or 1 major and one minor symptom.
5. Recovery time is calculated as the number of days from exacerbation e-diary signal onset (included) to exacerbation e-diary signal end (not included).

7.1.9. Time between 2 e-diary signals for exacerbations/evaluation of baseline symptom score:

The minimum duration between 2 e-diary signals with distinct baseline value is 15 days, which is the minimal period for which a new full exacerbation-free baseline can be calculated for the next e-diary episode.

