If a new worsening of symptoms occurs between 6 and 14 days of a previous exacerbation, the baseline period used will be the same baseline as the one of the original exacerbation. Therefore, it will last until the daily symptom count score has gone below the baseline symptom score of the previous event.

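### A visit made within the allowed 96 hours can be coded absent or delayed, because SAP 7.1.11.2 matches it to a calculated diary episode that can last only 2 to 4 days; three special episode-end rules also misfire

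*SAP*

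**What the plan says.** SAP references are to Amendment 1.

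- **Matching (7.1.11.2).** Case A is an alert with "no exacerbation visit within the calculated length of the e-diary episode". Case B is the reverse, a visit without a matching alert: "RDE exacerbation not within e-diary exacerbation period".
- **Episode length (7.1.8).** Item 1 ends an episode on the day the centred 3-day moving average of the symptom score returns to baseline, the mean score over days 14 to 8 before onset. A major symptom scores 2 and a minor one 1. Item 2 sets a floor: "The length of an e-diary signal of an exacerbation will be at least of 2 days". Item 5 counts the onset day but not the end day.
- **Visit window (Protocol 4.1 and 6.5.4, Table 9 footnote 4).** The AECOPD visit takes place as soon as possible after onset, "maximum 96 hours after and, if applicable, preferably before starting treatment with antibiotics".
- **Special end rules.** For a new worsening 6 to 14 days after an earlier exacerbation (7.1.9), "it will last until the daily symptom count score has gone below the baseline symptom score of the previous event". After more than 2 consecutive missing days (7.1.10 item 5), the signal stays unresolved "until the next day with observed data if the corresponding moving average is below the baseline value". For a first signal before day 3 (7.1.8 item 4), "duration will be counted until the day in which there is at most 2 majors or 1 major and one minor symptom".
- **What counts as an event.** 7.1.11.1 restricts the primary analysis to clinically confirmed unscheduled visits, with or without a signal. 7.1.11.2 then says that a Case A qualifies as an AECOPD when the site gives reason 3, or in some instances reason 4, and that every site-confirmed Case B qualifies.

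**The concern.** The matching window is set by how long the diary symptoms last, not by how long the protocol gives the site to see the subject. For a short episode the first can close before the second, so a site that met the protocol is recorded as having a missing or late visit.

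The special end rules can err the other way. An episode that never closes would match any later visit, and one that closes too early adds to the first problem.

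SAP 6.1.4 tabulates alerts with and without corresponding visits, confirmed AECOPD with and without alerts, and the agreement between clinical and diary-defined periods. Protocol 1.2.2.1 says that information from the AECOPD contacts will help refine the case definition of AECOPD. Discordance created by the matching rule would feed into that work as if it were a property of the diary.

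**Working it through.** **Inputs.** Onset is day 1. The diary needs two consecutive days of worsening (Protocol 4.1), so the alert cannot fire before day 2. Ninety-six hours is 4 days, so compliant visits after the alert fall on days 2 to 5. A qualifying day scores at least 2 + 1 = 3.

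**The plan's own figure.** Item 1 applies only from day 3, so the earliest end day is 3 and the shortest length is 3 − 1 = 2 days. This reproduces the stated floor.

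**General rule.** The end is the first day d ≥ 3 with [s(d−1) + s(d) + s(d+1)]/3 ≤ b, where s is the daily score and b the baseline. Length is d − 1.

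| Score pattern | Baseline b | End day | Length | Compliant days outside |
|---|---|---|---|---|
| 2 days at b+3, then b | 0, 1, 2 or 3 | 4 | 3 | 4, 5 |
| 3 days at b+3, then b | 0, 1, 2 or 3 | 5 | 4 | 5 |
| 4 days at b+3, then b | 0, 1, 2 or 3 | 6 | 5 | none |
| 2 days at 3, then 0 | 0.5 | 4 | 3 | 4, 5 |
| 2 days at 3, then 0 | 1 | 3 | 2 | 3, 4, 5 |
| 5 days at 3, then 0 | 2 | 5 | 4 | 5 |

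First row: on day 3 the average is (b+3 + b + b)/3 = b + 1, still above b. On day 4 it is b, so the length is 4 − 1 = 3.

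Length 2 needs the mean of days 2, 3 and 4 to be at or below b. If day 2 is above b, days 3 and 4 must average less than b. The fifth row shows this: (3 + 0 + 0)/3 = 1 = b. The subject has to fall under the usual level, not merely return to it.

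**Rules that require a score below baseline.** Scores cannot be negative, so at b = 0 the condition s < 0, or moving average < 0, is never met. At b = 1, 2 or 3 a subject who returns exactly to baseline and stays there also never meets it. The general rule does end at b = 0: events of 2, 3, 4 and 5 days have lengths 3, 4, 5 and 6. Section 7.1.9 also refers to the daily score, where the general rule uses the moving average.

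**7.1.8 item 4.** It ends the episode on a day with two major symptoms, or one major and one minor. 7.1.7 item 1 starts an episode with at least two symptoms, at least one of them major. A subject can satisfy both on the same day.

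**Case A and laboratory data.** 7.1.11.2 says no laboratory data are collected for a Case A. Protocol Table 8 schedules blood and sputum sampling at the AECOPD visit. An on-time visit after a short episode contradicts that sentence, which suggests the outcome was not intended.

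**The case against.** Sites review every mismatch, and reason 4 lists a delayed visit among its examples, so the mismatch is visible and explained. That stands in part. For a confirmed, on-time visit, reasons 1 to 3 do not fit, and reason 4 would record as delayed a visit that was not.

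The wording in 7.1.9 and 7.1.10 item 5 may simply be loose. The latter goes on to explain that days with a missing average count towards duration. This is a fair reading of intent, but a program written from the text would apply the strict condition.

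The agreement table compares clinical and diary periods, so the Case A window does not enter it directly. That stands; it is exposed only to the end rules. Item 4 covers only a first signal before day 3, far from the efficacy period that starts 1 month post-Dose 2. That stands too.

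A reader might infer three stronger points, none of which the documents support:

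- *Episodes never end when baseline is 0.* This is true only of the two rules that require a score below baseline. The general rule accepts equality.
- *One illness is counted twice and inflates AECOPD rates.* 7.1.11.1 rules this out for the primary analysis. Elsewhere it would need the site to choose reason 3 or 4, a chosen reason 4 to fall among those that qualify, and the visit to be counted separately as well. Whether that visit is also a Case B depends on whether visit date or recorded onset is tested, which 7.1.11.2 does not say.
- *Three of the four compliant days are typically lost.* That needs length 2, which a plain return to baseline does not produce.

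**Conclusion.** The point holds in limited form. A visit within the protocol's 96 hours can be coded absent or delayed whenever the calculated episode lasts 2 to 4 days. With a plain return to baseline, 2 of the 4 compliant days (2 to 5) fall outside for a 2-day event, 1 of 4 for a 3-day event, and none for longer events. These are counts of days, not a misclassification rate. The documents give no frequency of short episodes, visit timing or zero baselines, so the share of alerts affected cannot be computed.

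The end rules in 7.1.9 and 7.1.10 item 5 cannot be met at baseline 0 and conflict with the general rule. Item 4 of 7.1.8 conflicts with the onset criterion. Sections 7.1.11.1 and 7.1.11.2 leave open which analysis, if any, counts a Case A.

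This rests on a literal reading of the rules, onset taken as day 1, and the alert and visit tables in 6.1.4 using the Case A definition. AECOPD endpoints are tertiary (Protocol 11.3) and comparisons descriptive (Protocol 11.13), so exploratory tables are affected and no confirmatory conclusion is. It should still be corrected, because those tables are meant to inform the case definition.

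**What to change.** - **7.1.11.2, matching.** Treat an alert as matched if a confirmed AECOPD visit falls between e-diary onset and the later of onset plus 96 hours or episode end. Overlap of the eCRF onset-to-end interval with the diary episode is an acceptable alternative. Allow one AECOPD per matched pair.
- **7.1.9 and 7.1.10 item 5.** Require the 3-day moving average to be at or below baseline, as in 7.1.8 item 1.
- **7.1.8 item 4.** End the episode on the first day that no longer meets the onset criterion.
- **7.1.11.1 and 7.1.11.2.** Reconcile them: a Case A counts only where no confirmed visit exists for the same episode. Name the analysis in which it counts, and list which reason 4 specifications qualify.

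The cost is SAP text and programming; no new data are needed. The wider window may link a few unrelated alerts and visits.

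### SAP 7.1.11.1 limits AECOPD events to confirmed visits, but 7.1.11.2 lets some unconfirmed diary alerts qualify, with no criterion for reason 4 and no analysis named for the wider set

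*SAP*

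**What the plan says.** SAP Amendment 1, section 7.1.11.1, notes that the diary device can give false alerts and can miss exacerbations. It concludes that "only unscheduled AECOPD visits with clinical confirmation of AECOPD (with or without associated signals) will be considered as AECOPD events in the primary analysis". It then lists what a missed AECOPD visit may be: a diary signal without a visit that reconciliation could not discount, or "an exacerbation reported retrospectively in the Safety database or medical records" with no matching visit. It does not say whether either is analysed anywhere.

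Section 7.1.11.2 reconciles diary alerts with visits. Case A is an alert with an absent or delayed exacerbation visit; Case B is an exacerbation visit with an absent or delayed alert. For Case A, "The different reasons of inconsistencies of Case A will be categorized by the site after review according to the following explanation". Reason 3 is a technical problem, noticed when it was "too late to determine whether this was an exacerbation or not". Reason 4 is other reasons, to be specified, with examples including "subject unable to visit the site / delayed RDE visit/early RDE entry". The counting rule for Case A is that "if the answer about the inconsistency is 3) or sometimes 4) (depending on the specification), it will qualify as AECOPD". For Case B, "All Cases B will be considered to be an AECOPD if the AECOPD is confirmed by the site"; one Case B reason is "Planned monthly visit clinically deemed exacerbating".

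Section 7.1.7 refers the reader to 7.1.11 as a whole for the derivation of AECOPD. Sections 6.1.3 (incidence, VE, Cox model) and 6.1.4 (time to first AECOPD) cite neither subsection and label no AECOPD analysis as primary or sensitivity.

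In the protocol, the investigator confirms each AECOPD at the visit (4.1), and the dates of confirmed AECOPD are recorded in the eCRF (4.1.1).

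**The concern.** An alert under reason 3 cannot meet a clinical-confirmation requirement, because the site could not tell what it was. One subsection excludes it and the next says it qualifies. For reason 4 the plan does not say which specifications qualify, who decides, or when. Two programmers could build different AECOPD datasets from the same SAP text.

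The choice would reach four results: all-cause any-severity incidence and VE; time to first AECOPD; the 6.1.4 exclusion of subjects who exacerbate before 1 month post-Dose 2; and the 7.1.3 exclusion from the NTHi-associated analyses of subjects with an AECOPD but no sputum. Under 7.1.3, a subject whose only AECOPD is an unsampled alert contributes zero NTHi events under one rule and is removed under the other.

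Timing adds a reason to settle this early. SAP 8.1 runs AECOPD analyses in parallel with the Day 90 step, when the project statistician is unblinded.

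**Working it through.** **Step 1. Compare the two rules by type of event.**

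| Event | 7.1.11.1 | 7.1.11.2 |
|---|---|---|
| Confirmed at an unscheduled visit, with or without an alert | counts | counts |
| Confirmed at a visit later than the diary episode | counts | counts (also fits Case B) |
| Confirmed at a scheduled visit | counts, since protocol 6.5.3 records it as an AECOPD visit; only the word unscheduled clashes | counts (reason 6) |
| Alert, no confirmed visit, reason 3 | no | counts |
| Alert, no confirmed visit, reason 4 | no | sometimes, no criterion |
| Retrospective report, no visit | no | not addressed |

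The conflict lies in the reason 3 and reason 4 rows. A delayed visit fits both Case A and Case B, so the text should also say that one episode counts once.

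**Step 2. Which endpoints can move.** Section 7.1.11.2 states that Case A has no laboratory data, and 7.1.4 requires culture and then PCR for NTHi association. Alerts without a visit therefore cannot be NTHi-positive. Section 7.1.12 takes severity from the CRF, so an alert with no visit would normally carry no grade for the moderate/severe endpoints. What moves is the all-cause any-severity results and the two exclusions.

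**Step 3. Illustrative size.** The plan gives no AECOPD rate, VE or alert frequency, so it has no figure of its own to reproduce here. From the plan: n = 70 per group. Assumed: r = 1.5 confirmed events per control subject-year; true VE = 30%; a = 0.1, 0.3 or 0.5 retained alerts per subject-year; q = share of alerts unrelated to any vaccine effect.

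Observed VE = VE × (r + a(1 − q)) / (r + a).

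- q = 1: 0.30 × 1.5/1.6 = 28.1%; 0.30 × 1.5/1.8 = 25.0%; 0.30 × 1.5/2.0 = 22.5%.
- q = 0.5: 0.30 × 1.55/1.6 = 29.1%; 0.30 × 1.65/1.8 = 27.5%; 0.30 × 1.75/2.0 = 26.3%.

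The fall is about 1 to 7.5 points.

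For scale, expected confirmed events over one year are 70 × 1.5 = 105 in controls and 70 × 1.05 = 73.5 in the vaccine group. With SE(log RR) = √(1/105 + 1/73.5 + 2k/70), where k is the negative binomial dispersion, the 95% CI around a VE of 30% is:

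- k = 0 (Poisson): 6% to 48%
- k = 0.5: −2% to 52%
- k = 1: −9% to 55%

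**Step 4. Exclusions.**

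Before Day 90 (Poisson, t = 90/365.25 years, no vaccine effect yet), the excluded share is 1 − exp(−(r + a)t). It is 30.9% with no alerts and 32.6%, 35.8% or 38.9% with them. That is about 2, 7 or 11 more of 140 subjects.

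For the sputum exclusion, assume one year, every confirmed event sampled, no alert sampled, and exclusion only if no AECOPD was sampled. The number newly excluded is 70 × P(no confirmed event) × (1 − exp(−a)).

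- Poisson, control: 70 × exp(−1.5) × (1 − exp(−a)) = 1.5, 4.0, 6.1.
- Poisson, vaccine: 70 × exp(−1.05) × (1 − exp(−a)) = 2.3, 6.3, 9.6.
- Negative binomial with k = 1, control: P(no event) = 1/2.5, giving 2.7, 7.3, 11.0.
- Negative binomial with k = 1, vaccine: P(no event) = 1/2.05, giving 3.2, 8.9, 13.4.

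If the vaccine works, the loss is larger in the vaccine group, because more of its subjects have no confirmed event.

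**The case against.** The strongest reply is that the plan does assign a rule. Section 7.1.11.1 is the definition section and ties confirmed visits to the primary analysis. Section 7.1.11.2 concerns inconsistencies and has its own use in the 6.1.4 tables of alerts with and without visits. On that reading the defect is one loose sentence and one undefined term. Much of this stands: a reader might infer that no section prefers either rule, and that is not so. It does not remove the conflict. Section 7.1.11.2 goes beyond tabulation to say that these alerts qualify as AECOPD, the primary endpoints of this study are safety endpoints, and no analysis is named for the wider set.

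Other stronger readings fail:

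- **Planned-visit events as a second conflict.** Case B requires site confirmation and protocol 6.5.3 has such events recorded as AECOPD visits, so they count under either rule.
- **Delayed visits adding NTHi-positive or graded events.** A confirmed visit counts under both rules, so choosing between them adds none.
- **Retrospective reports lacking any rule.** The word only in 7.1.11.1 already leaves them out of the primary analysis. What is open is whether they appear elsewhere.
- **Event selection by the unblinded statistician.** The documents do not say this. Sites assign the reason, and site evaluators are blinded (protocol 6.3).

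It is also fair that every rate above is assumed, that the top alert rate is a third of the confirmed rate, and that sputum is taken only if judged safe, so not every confirmed event would be sampled. The annex of tables, figures and listings was not among the documents and may name event sources; the SAP text does not.

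**Conclusion.** The concern holds in limited form. The two subsections give event sets that differ by diary alerts without a confirmed visit; the reason-4 rule cannot be applied as written; and the analysis sections do not say where the wider set belongs.

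The size is unknown. Under the assumed rates, VE on all-cause any-severity AECOPD shifts by about 1 to 7.5 points, well inside its confidence interval. The two exclusions change by a few subjects to around a dozen, and the sputum exclusion does so unequally between groups if the vaccine works. The NTHi analyses can lose subjects but cannot gain events by this route.

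The endpoints are tertiary and the comparisons descriptive (protocol 11.13), so what is at stake is interpretability and reproducibility, not a decision rule. Priority is modest, but this is a contradiction in the text, not merely a missing detail.

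**What to change.** In SAP 6.1.3, 6.1.4 and 7.1.11, state that incidence, VE, time to first AECOPD, the pre-Day 90 exclusion and the 7.1.3 sputum exclusion all use investigator-confirmed AECOPD recorded in the eCRF. Say that this holds whether the visit was unscheduled, coincided with a scheduled visit or was delayed beyond the diary episode, and that each episode counts once. This also resolves the word unscheduled and the undefined primary analysis.

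Place unconfirmed Case A alerts (reason 3 and listed reason-4 specifications) and unconfirmed retrospective reports only in a named sensitivity analysis of all-cause any-severity AECOPD. Replace the open wording on reason 4 with a list of qualifying specifications, fixed before the first data lock point and applied by blinded personnel. The adjudication committee that protocol 4.3 allows could do this.

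The cost is SAP wording and one sensitivity analysis, with no new data. The downside is that some true but unconfirmed exacerbations leave the main count; the sensitivity analysis shows how much that matters.
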